Appendix G Abbreviations

Abbreviation or special term	Explanation
5-LO	5-lipoxygenase
ABPM	Ambulatory Blood Pressure Monitoring
ACEi	Angiotensin Converting Enzyme Inhibitors
ACR	Albumin to Creatinine Ratio
AE	Adverse Event
ALT	Alanine Aminotransferase
ALP	Alkaline Phosphatase
ANCOVA	Analysis of Covariance
AST	Aspartate Aminotransferase
ARB	Angiotensin Receptor Blocker
AZRand	AstraZeneca randomisation solution
BA	Bioavailability
CCI	
BMI	Body Mass Index
BP	Blood Pressure
CAD	Coronary Artery Disease
CONSORT	Consolidated Standards of Reporting Trials
COVID-19	Coronavirus Disease-2019
CCI	
CKD	Chronic Kidney Disease
CKD-EPI	Chronic Kidney Disease Epidemiology Collaboration
CRO	Contract Research Organisation
CSP	Clinical Study Protocol
CSR	Clinical Study Report
DDI	Drug-Drug interaction
DILI	Drug-Induced Liver Injury
DKA	Diabetic Ketoacidosis
DKD	Diabetic Kidney Disease
DNA	Deoxyribonucleic Acid
DM	Diabetes Mellitus
CCI	
EC	Ethics Committee, synonymous to Institutional Review Board (IRB) and Independent Ethics Committee (IEC)
ECG	Electrocardiogram

Abbreviation or special term	Explanation
eCRF	electronic Case Report Form
EDC	Electronic Data Capture
eGFR	Estimated Glomerular Filtration Rate
EMA	European Medicines Agency
CCI	[REDACTED]
FDA	U.S. Food and Drug Administration
FLAP	5-Lipoxygenase Activating Protein
FSH	Follicle Stimulating Hormone
fT3	Free triiodothyronine
fT4	Free thyroxine
GCP	Good Clinical Practice
GLP1-RA	Glucagon-like peptide-1 Receptors Agonists
HbA1c	Glycated Haemoglobin
hCG	Human Chorionic Gonadotropin
HIPAA	Health Insurance Portability and Accountability Act
HL	Hy's Law
HR	Heart rate
CCI	[REDACTED]
IATA	International Airline Transportation Association
IB	Investigator's Brochure
ICH	International Council for Harmonisation
ICF	Informed Consent Form
IgG	Immunoglobulin G
CCI	[REDACTED]
IMP	Investigational Medicinal Product
INR	International Normalised Ratio
IRT	Interactive Response Technology
IVRS	Interactive Voice Response System
IWRS	Interactive Web Response System
LH	Luteinising Hormone
CCI	[REDACTED]
MedDRA	Medical Dictionary for Regulatory Activities

Abbreviation or special term	Explanation
NSAID	Non-Steroidal Anti-Inflammatory Drug
CCI	[REDACTED]
OTC	Over the Counter
PD	Pharmacodynamics
PHL	Potential Hy's Law
PK	Pharmacokinetic
CCI	[REDACTED]
PT	Preferred Term
QTc	Corrected QT interval
RTSM	Randomization and Trial Supply Management
SAE	Serious Adverse Event
SAP	Statistical Analysis Plan
SARS-CoV-2	Severe Acute Respiratory Syndrome Coronavirus 2
SBP	Systolic Blood Pressure
SCr	Serum Creatinine
SD	Standard Deviation
SMAD	Single-Multiple Ascending Dose
SoA	Schedule of Activities
SOC	System Organ Class
SGLT2i	Sodium-Glucose Cotransporter-2 inhibitor
SUSARs	Suspected Unexpected Serious Adverse Reactions
T1DM	Type 1 Diabetes Mellitus
T2DM	Type 2 Diabetes Mellitus
TSH	Thyroid stimulating hormone
ULN	Upper Limit of Normal
WHO	World Health Organisation

Appendix H Protocol Amendment History

DOCUMENT HISTORY	
Document	Date
Version 2.0, Amendment 1	05-Aug-2020
Version 1.0	29-May-2020

The Protocol Amendment Summary of Changes Table for the current amendment (Amendment 2) is located directly before the Table of Contents.

Amendment 1 (05-August-2020)

This amendment is considered to be substantial based on the criteria set forth in Article 10(a) of Directive 2001/20/EC of the European Parliament and the Council of the European Union.

Overall Rationale for the Amendment

The original CSP, Final 1.0, dated 29 May 2020, is updated following the FDA safety review (10 Jul 2020) and updates have been made to correct errors and further clarify processes.

Section # and Name	Description of Change	Brief Rationale
Section 1.1, Synopsis Section 3, Objectives and Endpoints	Coagulation is included to the laboratory parameters for the secondary endpoint: To evaluate the safety and tolerability of AZD5718 in participants with proteinuric CKD	Omitted in error, included for consistency
Section 1.1, Synopsis Section 4.1, Overall design	The number of countries included in the study are updated from 10 to 12	Additional countries will be included in the study
Section 1.1, Synopsis Section 1.3, Table 1 Schedule of Activities Section 4.1, Overall design Section 8.1.1.1, Urinary Albumin Creatinine Ratio	Clarification of how the ACR result is calculated to determine exclusion of participants from Treatment Period 2	Process clarification
Section 1.3, Table 1 Schedule of Activities	Abbreviated physical examinations are not completed at Visits 5 and 7 (X removed)	A full physical examination is required at these visits; both abbreviated and full were included at these visits in error
Section 1.3, Table 1 Schedule of Activities Section 8.2.4 Clinical Safety Laboratory Assessments, Table 4	Footnotes to clarify that serum hCG, FSH, and LH tests, and a urine pregnancy test are required for all women, not only women with intact uterus	Increasing clarity of pregnancy testing approach in response to feedback from trial sites

Section # and Name	Description of Change	Brief Rationale
Section 1.3, Table 1 Schedule of Activities	Coagulation is included in the safety laboratory assessments row	Omitted in error
	Deletion of duplicate row for urinalysis assessments (safety laboratory assessments)	Duplicate row included in error
Section 1.3, Table 1 Schedule of Activities	Sampling timepoints for plasma and urine CCI are reduced; samples will not be collected at Visits 2, 4, 6, and 10	Changes to the plan for analysis of CCI
	The correct footnote is applied to the row: Reminder to collect first morning void urine samples, 3 days before visit (Site should follow-up directly with the participant via phone to remind the participant)	Incorrect footnote included in error
	The correct footnote is applied to the row: Study drug dispensation (Study drug refers to AZD5718/placebo during Treatment Period 1 and AZD5718/placebo + dapagliflozin during Treatment Period 2)	Incorrect footnote included in error
Section 1.3, Table 1 Schedule of Activities Section 8.2.4, Clinical safety laboratory Assessments	Note is included to clarify the local and central laboratory assessment procedures. Section 8.2.4 is updated to clarify the use of local urine dipstick tests	Process clarification
Section 1.3, Table 1 Schedule of Activities Section 8.2.2, Vital Signs	Pulse oximetry is included in the vital signs assessments	FDA request to monitor oxygen saturation to check for respiratory depression
Section 1.3, Table 1 Schedule of Activities Section 8.1.3, CCI	CCI	Process clarification
Section 1.3, Table 1 Schedule of Activities Section 6.4.1	Text added to clarify that where completion of an e-Diary is not applicable, participant will be requested to complete a paper dosing diary Details of an e-Diary satisfaction survey added	Process clarification

Section # and Name	Description of Change	Brief Rationale
Section 5.1, Inclusion Criterion #5	Clarification that females must be of non-childbearing potential and that a pregnancy test is required for all female participants	Process clarification
Section 5.1, Inclusion Criterion #6 Section 8.3.8.2, Paternal Exposure	Text added to clarify the contraceptive requirements for male participants in regions where male condoms with spermicide are not available	Process clarification
Section 5.2, Exclusion Criterion #6 (h)	Clarification that alcohol and drug screening is completed locally using laboratory kits provided by the central laboratory, and that screening must be completed for all participants	Process clarification
Section 6.1.1 Investigational Products, Table 3	Table updated stating that Dapagliflozin is taken once daily	Clarification
Section 6.5.2, SGLT2 Inhibitors	Clarification of SGLT2i fixed-dose combination treatments allowed during Treatment Period 2	Clarification
Section 7.1, Discontinuation of Study Drugs	Greater than (>) is changed to \geq for ALT, AST, and total bilirubin where the CSP refers to Hy's Law	Consistency with Hy's Law Appendix E
Section 8.2.4, Clinical Laboratory Assessments	Additional safety samples do not need to be recorded in the eCRF	Process clarification
Section 9.4.3, Safety (Statistical Analyses)	Coagulation and urinalysis are included in the description of the statistical analysis for laboratory safety tests	Omitted in error, included for consistency
Throughout	Minor editorial and document formatting revisions	Minor, therefore have not been summarised

4.12	Interim Analysis	32
4.12.1	Early Termination of Study	32
4.13	Determination of Sample Size	32
4.14	Changes in the Conduct of the Study or Planned Analysis	32
5	REFERENCES	34
6	APPENDIX	35
	Appendix A: Schedule of Activities	36
	Appendix B: Interim Analysis Plan	39
	Appendix C: Treatment-Emergent Laboratory and Vital Signs Criteria limits	42
	Appendix D: Exclusion from Per-Protocol Analysis	43

REVISION HISTORY

Version No.	Effective Date	Summary of Change(s)
1.0	15 OCT 2020	Original document
2.0	26 APR 2022	
Addition of Ambulatory Blood Pressure Monitoring (ABPM) analyses for day-time/night-time, and hourly ABPM Mixed Models for Repeated Measures. Sub-group and sensitivity analyses added.
 
Appendix D added to include Multiple Imputation (MI) for ABPM data.
 
Update to Appendix D to clarify that MI will be performed using hourly mean Systolic Blood Pressure (SBP) measurements.
 
Statistical modelling for the hourly mean SBP will be based on the change of hourly mean SBP.
 
Sensitivity analysis of the ABPM analysis for participants with treatment compliance $\geq 80\%$ added.
 
By-strata efficacy analysis added for urine albumin to creatinine ratio (UACR) and estimated glomerular filtration rate (eGFR).

3.0	27 SEP 2022	
Following early termination of study, planned analysis is updated to reflect analysis of interest for final clinical study report. Removal of AZD5718 pharmacokinetic (PK) analysis, Dapagliflozin PK analysis, biomarker analysis and ABPM sensitivity analysis.
 
Addition of Changes from Planned Analysis section which outlines the differences between the study protocol and the statistical analysis plan following the study termination.

LIST OF ABBREVIATIONS

Abbreviation/Acronym	Definition/Expansion
5-LO	5-lipoxygenase
ABPM	Ambulatory Blood Pressure Monitoring
ACR	Albumin to Creatinine Ratio
AE	Adverse Event
ALT	Alanine Aminotransferase
ANCOVA	Analysis of Covariance
AST	Aspartate Aminotransferase
CCI	
BMI	Body Mass Index
BMP	Blinding Maintenance Plan
BP	Blood Pressure
CI	Confidence interval
CKD	Chronic Kidney Disease
COVID-19	Coronavirus Disease of 2019
CSP	Clinical Study Protocol
CSR	Clinical Study Report
CST	Central Subfield Thickness
DBL	Database Lock
DBP	Diastolic Blood Pressure
DKD	Diabetic Kidney Disease
DM	Diabetes Mellitus
ECG	Electrocardiogram
eCRF	electronic Case Report Form
eGFR	Estimated Glomerular Filtration Rate
CCI	
FAS	Full Analysis Set
FCS	Fully Conditional Specification
FLAP	5-Lipoxygenase Activating Protein
HR	Heart rate
CCI	
CCI	
IMP	Investigational Medicinal Product
IPD	Important protocol deviations
LOCF	last observation carried forward
CCI	
MCP-Mod	Multiple Comparison Procedure – Modelling
MedDRA	Medical Dictionary for Regulatory Activities
MI	Multiple Imputation
MMRM	Mixed Model for Repeated Measures
CCI	
PD	Pharmacodynamic
PEY	Participant Exposure Year
PK	Pharmacokinetic(s)
PP	Per-Protocol
CCI	
PT	Preferred Term
SAE	Serious Adverse Event
SAP	Statistical Analysis Plan
SBP	Systolic Blood Pressure
SD	Standard Deviation
SGLT2i	Sodium-Glucose Cotransporter 2 inhibitors

Abbreviation/Acronym	Definition/Expansion
SoA	Schedule of Activities
SOC	System Organ Class
T2DM	Type 2 Diabetes Mellitus
TELVC	Treatment-emergent laboratory and vitals change
UACR	Urine Albumin to Creatinine Ratio

1 INTRODUCTION

Chronic kidney disease (CKD) is a worldwide public health problem associated with significant morbidity and mortality; diabetes mellitus (DM) is the leading cause of end-stage renal disease. The pathophysiology of diabetic kidney disease (DKD) is multifactorial, with both haemodynamic effects contributing to glomerulofibrosis and inflammation emerging as major contributors to disease progression. CCI

While it is anticipated that sodium-glucose cotransporter 2 inhibitors (SGLT2i) will be a key component of standard of care for proteinuric CKD in the future, definitive evidence in non-diabetic CKD is anticipated, but not yet available, and current uptake in DKD is limited with fewer than 5% of participants on SGLT2i treatment.

This Phase 2b study will investigate if AZD5718, a FLAP inhibitor, can reduce albuminuria in participants with proteinuric CKD both on treatment with dapagliflozin as future standard of care and on current standard of care with minimal SGLT2i use. The dose-response relationship, and the safety and pharmacokinetic (PK) profile of AZD5718 will be evaluated. Following the early termination of the FLAIR study, details for changes to analysis are included in Section 4.14.

The results of the study will form the basis for the future clinical development programme for AZD5718. The primary endpoint for this study is based on anticipated future standard of care with all participants on the SGLT2i dapagliflozin. Efficacy, and safety on current standard of care with limited use of SGLT2i are secondary endpoints

This statistical analysis plan (SAP) documents the variables to be analysed and the methods of analyses planned. The analyses of the following variables will be reported outside the clinical study report (CSR) and are therefore outside the scope of this SAP:

- CCI
- CCI

An electronic Case Report Form (eCRF) will be used to capture participant data into a secure, validated database. The following data are captured outside the eCRF and will be transferred electronically into the database periodically during the study:

- Safety laboratory data
- Electrocardiogram (ECG) data
- AZD5718 concentration in plasma
- E-Diary

The analyses described in this SAP are based upon the following study documents:

- Study Protocol, Version 3.0 (25 JAN, 2021)
- eCRF, Version 2.0 (12 OCT, 2020)

2 STUDY OBJECTIVES

2.1 Primary Objective

Primary Objective	Estimand Description
To evaluate the dose-response effect of AZD5718 on urine ACR at 20 weeks in participants with proteinuric CKD (on treatment with dapagliflozin as future standard of care from Weeks 12 to 20)	Reduction of urine ACR from baseline to Week 20 compared with placebo. The primary estimand is a hypothetical estimand such that the treatment effect is quantified in the optimal situation where any potential confounder is avoided. The population of interest is the Per-Protocol population. The endpoint being assessed is the change in log-transformed urine ACR from baseline to Week 20. For the intercurrent event, if a participant discontinues treatment due to AE or lack of efficacy, or uses prohibited medication, the urine ACR data are treated as missing after the event and no imputation is performed. The summary measure being evaluated is the geometric mean reduction of urine ACR from baseline to Week 20.

[figure not shown]
Abbreviations: ACR = albumin to creatinine ratio; AE = adverse event; CKD = chronic kidney disease.

2.2 Secondary Objectives

Secondary Objectives	Endpoints
To evaluate the dose-response effect of AZD5718 on urine ACR at 12 weeks (on current standard of care)	Reduction of urine ACR from baseline to Week 12 compared with placebo. The clinical quantity of interest to be estimated is defined by the following three components: 
 Population Randomised participants who meet all eligibility criteria and have valid non-missing urine ACR records at baseline and at least one post-treatment visit. Endpoint Change in log-transformed urine ACR from baseline to Week 12. Summary measure Geometric mean reduction of urine ACR from baseline to Week 12 compared with placebo.
To evaluate the safety and tolerability of AZD5718 in participants with proteinuric CKD	
 AEs/SAEs Vital signs Clinical chemistry/ haematology/urinalysis parameters ECG assessments
To evaluate the effect of AZD5718 on ambulatory blood pressure in participants with proteinuric CKD	Change in 24-hour mean SBP from baseline to Week 12.
To assess the PK of AZD5718 after repeated oral dosing for 20 weeks in participants with proteinuric CKD	AZD5718 plasma concentrations [Note: following the termination of FLAIR study, the PK analyses will not be performed]
To assess the effect of AZD5718 on renal function in participants with proteinuric CKD with and without the addition of dapagliflozin	Change in eGFR from baseline to Week 12 and from Week 12 to Week 20.

Abbreviations: ACR = albumin to creatinine ratio; AE = adverse event; CKD = chronic kidney disease; ECG = electrocardiograms; eGFR = estimated glomerular filtration rate; PK = pharmacokinetic(s); SBP = systolic blood pressure; SAE = serious adverse event.

Figure 1 Study Design

R = randomisation

The total duration of the study will be at least 28 weeks for each individual participant. Following early termination of the study, participants will have a total study duration of up to 28 weeks.

It is planned to have approximately 568 evaluable participants (142 per group) completing the study. Randomisation will be stratified by diabetes status (DKD and non-DKD) at the time of randomisation in order to ensure approximate balance between treatment groups within each sub-population. The strata are:

- Stratum 1: DKD participants without SGLT2i background outside Japan
- Stratum 2: DKD participants with SGLT2i background outside Japan
- Stratum 3: Non-DKD participants outside Japan
- Stratum 4: DKD participants without SGLT2i background in Japan
- Stratum 5: DKD participants with SGLT2i background in Japan
- Stratum 6: Non-DKD participants in Japan

The number of randomised DKD and non-DKD participants will be monitored in order to ensure that the non-DKD sub-population is 30% to 35% of the total participants randomised. At least 72 Japanese participants will be included.

The primary objective is to determine the efficacy of AZD5718 as assessed by change from baseline in urine albumin to creatinine ratio (ACR) at Week 20, when compared to placebo as defined in Section 4.9.2.

The study schedule of activities (SoA) is available in [Appendix A](#).

An administrative interim analysis will be conducted when approximately 200 participants have completed the 20-week treatment period. For further details, see Section 4.9.1.5.

3.2 Endpoints

For a full list of all study assessments and the timings of the assessments, see the SoA in [Appendix A](#)

3.2.1 Efficacy Variables

3.2.1.1 Urine ACR

Urine ACR is a key marker for assessing kidney damage. Urine ACR is a ratio between measured albumin and measured creatinine, which estimates 24-hour urine albumin excretion. See the SoA in [Appendix A](#) for timing of collection.

Urine ACR will be calculated as:

$$\text{Urine ACR (mg/g)} = \frac{\text{urine albumin (mg/dL)}}{\text{urine creatinine (g/dL)}}$$

Spot urine samples are collected during the Screening Visit and at the remaining timepoints, participants are required to collect first morning void urine samples on 3 consecutive days. At each visit, the geometric mean of the triplicate ACRs will be computed centrally and used for all analysis of urine ACR.

Baseline urine ACR is taken to be the geometric mean of urine ACR geometric mean measurements taken at Visit 2 (Screening Visit 2) and Visit 3 (Study Day 1).

3.2.1.2 Estimated GFR

Estimated GFR is a marker for assessing kidney function. Estimated GFR is calculated based on serum creatinine values and will be calculated by the central laboratory using the CKD-EPI equation as follows:

$$\begin{aligned} eGFR \text{ (mL/min/1.73m}^2\text{)} \\ &= 141 \times \min(SCr/\kappa, 1)^\alpha \times \max(SCr/\kappa, 1)^{-0.209} \times 0.993 \text{ Age} \\ &\times (1.018 \text{ if female}) \times (1.159 \text{ if Black}) \end{aligned}$$

Where SCr = serum creatinine (in mg/dL), κ is 0.7 for females and 0.9 for males, α is -0.329 for females and -0.411 for males, min indicates the minimum of SCr/ κ or 1, and max indicates the maximum of SCr/ κ or 1.

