5.1 Inclusion Criteria

Participants are eligible to be included in the study only if all of the following criteria apply:

Age

- 1 Participants must be ≥ 18 years of age inclusive, at the time of signing the informed consent.

For participants who haven't reached the age of maturity according to local regulations in their country, a written informed consent should be obtained from the participant and his or her legally acceptable representative.

Type of Participant and Disease Characteristics

- 2 Participants with proteinuric CKD defined as
 - eGFR 20 – 75 mL/min/1.73m² based on chronic kidney disease epidemiology collaboration (CKD-EPI) equation at Screening Visit 1 **and**
 - albuminuria defined as 200 -5000 mg albumin/g creatinine based on the geometric mean of the replicated measurements using 3 sequential first morning void urine at Visit 2.**and**
 - with diagnosis of T2DM (for **DKD sub-group only**).

Weight

- 3 Body weight within 50-150 kg and BMI within the range 18 to 45 kg/m² (inclusive).

Sex

- 4 Male or female
- 5 Female participants must be of non-childbearing potential and must have been surgically sterilised (ie, bilateral oophorectomy, and/or complete hysterectomy, and/or bilateral salpingectomy; tubal ligation is not sufficient) or be postmenopausal (amenorrhoeic for 12 months or more following cessation of exogenous hormonal treatments and assessed by serum follicle stimulating hormone [FSH] and luteinising hormone [LH] levels at Screening Visit 1). All female participants must have a negative serum pregnancy test at Screening Visit 1 and negative urine pregnancy test at Visit 3 (Day 1) prior to study drug administration.
- 6 Male participants must be surgically sterile or agree to use highly effective contraceptives. Non-sterilised male participants who are sexually active with a female partner of childbearing potential must use a male condom with spermicide from Day 1 to 3 months after the last dose of the study drug. It is strongly recommended for the female partner of a male participant to also use a highly effective method of contraception throughout this period.

Note: In case a male condom with spermicide is not available in a country or region, non-sterilised male participants who are sexually active with a female partner of childbearing potential must use a male condom without spermicide and the female partner should use a highly effective contraceptive method.

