 - ALT or AST $> 3 \times$ ULN with the appearance of fatigue, nausea, vomiting, right upper quadrant pain or tenderness, fever, rash, and/or eosinophilia ($> 5\%$)

If an unexpected, acute decline in GFR is observed ($> 15\%$ decrease in eGFR from the

Screening Visit values), the participant should be promptly evaluated. Volume depletion, hypotension, inter-current medical problems, and concomitant drugs may cause increases in blood creatinine. Urinary tract infection and urinary obstruction should be considered. Several drugs may cause a decline in GFR, especially NSAIDs and certain antibiotics such as trimethoprim. If any drug is suspected of causing or contributing to worsening kidney function, their use should be re-considered. The Investigator together with the Study Physician should consider the discontinuation of the investigational medicinal product (IMP) if eGFR decreases by more than 30% of Screening Visit values.

Consider temporary interruption of dapagliflozin if DKA is suspected. The participant should be promptly evaluated. If DKA is confirmed, dapagliflozin should be discontinued permanently.

Note that discontinuation from study drugs is NOT the same thing as a withdrawal from the study.

Participants who are permanently discontinued from receiving the study drugs will be followed for protocol-specified assessments, including follow-up of any AEs, unless consent is withdrawn specifically from further study participation (Section 7.2), the participant is lost to follow-up (Section 7.2), or the participant is enrolled in another clinical study.

A participant who decides and/or is recommended by the treating physician or the Investigator to permanently discontinue the study drugs will always be asked about the reason(s) for discontinuation and about the presence of any AEs. All efforts must be taken to ensure that the participant will be seen and assessed by an Investigator and, as scheduled for other participants, all end of treatment visit assessments should be completed at the time of discontinuation of study drug.

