8.1.2 Secondary Efficacy Assessments

8.1.2.1 Estimated Glomerular Filtration Rate

Estimated GFR is another marker that is considered as a standard for assessment of kidney function. It is calculated based on serum creatinine values using the widely validated and accepted CKD-EPI equation (Levey et al, 2009). Blood samples for estimation of serum creatinine are collected at various timepoints during the course of the study as shown in SoA (Table 1). Estimated GFR is then calculated as follows.

$$\begin{aligned} eGFR \text{ (mL/min/1.73 m}^2\text{)} \\ &= 141 \times \min(\text{Scr}/\kappa, 1)^\alpha \times \max(\text{Scr}/\kappa, 1) - 0.209 \times 0.993 \text{ Age} \\ &\times (1.018 \text{ if female}) \times (1.159 \text{ if Black}) \end{aligned}$$

Where: SCr = serum creatinine (in mg/dL); κ is 0.7 for females and 0.9 for males, α is -0.329 for females and -0.411 for males, min indicates the minimum of SCr/ κ or 1, and max indicates the maximum of SCr/ κ or 1.

Estimated GFR calculations will be performed by the central laboratory.

Alternatively, serum cystatin-C alone provides GFR estimates that are nearly as accurate as serum creatinine adjusted for age, sex and race thus providing an alternative GFR estimate that is not linked to muscle mass (Stevens et al, 2008). Blood samples will also be collected for measurement of cystatin-C at specified time points in the SoA (Table 1).

8.1.3

CCI

CCI [REDACTED]

CCI [REDACTED]

CCI [REDACTED]

[REDACTED]

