4.4.2 Protocol Deviations

Important protocol deviations (IPDs) are defined as those deviations from the protocol likely to have an impact on the perceived efficacy and/or safety of study treatments. The impact of IPDs on the efficacy and/or safety results will be investigated by assessing the robustness of the study results and conclusions to the choice of analysis set, both including and excluding data potentially affected by IPDs.

Important protocol deviations and any action to be taken regarding the exclusion of participants or affected data from specific analyses are defined in the project-specific Protocol Deviation Specification.

For this study, the following general categories will be considered IPDs and will be summarised in the CSR:

- Deviation 1: Participants who did not meet the Inclusion criteria or met Exclusion criteria and received study treatment.
- Deviation 2: Participants assigned to treatment who received their assigned study treatment at an incorrect dose at one or more occasions.
- Deviation 3: Participant received prohibited medication during study treatment period.
- Deviation 4: Met study treatment discontinuation criteria but continued study treatment and potentially had major impact to participants' safety according to clinical judgement.

- Deviation 5: Missed visits, assessments, or treatments that, in the Investigator's opinion, were due to the COVID-19 global pandemic and there was a significant effect on EITHER completeness, accuracy, and/or reliability of the participant's data, OR the participant's rights, safety or well-being.
- Deviation 6: Data in CRF not consistent with source documents and/or discrepancies are not explained.

The number and percentage of participants with any IPD will be summarised for each IPD category based on the full analysis set (FAS). Participants with more than one deviation in the same IPD category will be counted once for that IPD category. Any participants who have deviations in more than one IPD category will be counted once in the overall summary.

A list of all protocol deviations, including those reported by monitors, will be reviewed and decisions regarding how to handle these deviations will be documented by the study team physician, clinical pharmacology scientist and statistician prior to database lock (DBL). The final classification will be made prior to database lock.

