4.9.3.2 Estimated GFR

Estimated GFR will be analysed, comparing eGFR at baseline with that at 12 weeks, to determine whether there is any acute change with the introduction of AZD5718 to inform planning for a GFR slope analysis in Phase 3. This will be analysed using a by-visit ANCOVA, adjusting for DM stratification factor, treatment group and baseline eGFR. The FAS will be used for this analysis and eGFR will be evaluated on the original scale. The analysis will be repeated on the Per-Protocol Analysis Population.

The results of the by-visit ANCOVA will be presented by treatment group. A summary of change from baseline of eGFR results will be presented by treatment group and a by-participant listing provided of eGFR results at each visit. Plots of the least-squares mean by treatment group over time, and the mean eGFR over time up to follow-up visit will be presented.

An ANCOVA model will be produced for eGFR up to Week 20, analysed on the Per-Protocol Analysis set, similarly to that described above.

The analysis will also be repeated by strata (DKD without SGLT2i background, DKD with SGLT2i background, non-DKD), adjusting for treatment group and baseline eGFR.

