4.14 Changes in the Conduct of the Study or Planned Analysis

Following the results from the interim analysis, it was decided to terminate the study early and reduce the scope of analysis. This decision led to the removal of the MCP-Mod analysis as outlined in the protocol, and the previously described sensitivity analysis for the ABPM analysis. The statistical analysis plan has been updated to include only the analysis which will be performed following database lock.

Pharmacokinetic analyses of AZD5718 and dapagliflozin were also removed from the final analysis. The statistical analysis plan has been updated to reflect this.

Due to the early termination of the study, the total number of randomised participants is 613 with 340 participants completing treatment. Therefore, efficacy analyses should be evaluated with caution due to lack of power.

The total study duration, as highlighted in Section 3.1, will vary following study termination, up to a maximum of 28 weeks.

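### With the printed exponent of -0.209, eGFR cannot in practice fall below about 40, although the trial enrols participants at 20 to 75

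*SAP*

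**What the plan says.** SAP section 3.2.1.2 assigns eGFR to the central laboratory, names the CKD-EPI equation and sets out the formula to be applied. Its factor for creatinine above κ (0.7 mg/dL in women, 0.9 in men) is "\max(SCr/\kappa, 1)^{-0.209". Protocol section 8.1.2.1 has the same number, "\max(\text{Scr}/\kappa, 1) - 0.209", with the superscript apparently flattened in the extracted text. It cites the source publication and states: "Estimated GFR calculations will be performed by the central laboratory".

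eGFR is then used in several places:

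- Inclusion criterion 2 (Protocol section 5.1) requires eGFR of 20 to 75, "based on chronic kidney disease epidemiology collaboration (CKD-EPI) equation at Screening Visit 1".
- Protocol section 7.1 calls for prompt evaluation after a fall of more than 15%. It adds that the investigator and study physician "should consider the discontinuation of the investigational medicinal product (IMP) if eGFR decreases by more than 30% of Screening Visit values".
- SAP section 4.9.3.2 analyses eGFR as a secondary efficacy variable by ANCOVA: "The FAS will be used for this analysis and eGFR will be evaluated on the original scale".
- SAP section 4.6 tabulates baseline CKD stages down to Stage 4 (15–29 mL/min) and Stage 5 (below 15).

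**The concern.** The exponent above κ sets how fast eGFR falls as creatinine rises in a kidney disease population. At -0.209 the curve is flatter above κ than below it, where the plan's α is -0.329 for women and -0.411 for men. That raises the question whether the formula can produce the eGFR values the trial requires.

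If the printed form was programmed, or is used to check the laboratory's values, then eligibility, the eGFR ANCOVA and the 15% and 30% decline rules all rest on wrong numbers. The list of important protocol deviations would be affected too, because its first category (SAP section 4.4.2) is "Participants who did not meet the Inclusion criteria or met Exclusion criteria and received study treatment".

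**Working it through.** **Inputs from the documents.** The constants are 141; κ = 0.7 (women) or 0.9 (men); exponent -0.209 above κ; 0.993 raised to the power of age (reading age as a lost superscript); 1.018 if female; 1.159 if Black. The target is eGFR 20 to 75. The minimum age is 18, with no upper limit.

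**Assumptions not in the documents.** A creatinine ceiling of 15 mg/dL and an upper age of 90, both varied below.

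**Step 1: can the formula span 20 to 75?** At creatinine equal to κ, a man aged 60 has 141 × 0.993^60 = 92.5, so for him the whole enrolment range lies above κ. There eGFR is proportional to creatinine^-0.209, so age, sex and race cancel from the ratio:

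fold rise from 75 to 20 = (75/20)^(1/0.209) = **558**.

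**Step 2: values at age 60.** Man: 141 × (SCr/0.9)^-0.209 × 0.993^60. Woman: 141 × (SCr/0.7)^-0.209 × 0.993^60 × 1.018.

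| | SCr 2 | SCr 5 | SCr 10 | SCr 15 | SCr for eGFR 75 | SCr for eGFR 20 |
|---|---|---|---|---|---|---|
| Man | 78.3 | 64.6 | 55.9 | 51.4 | 2.46 | 1,370 |
| Woman | 75.6 | 62.4 | 54.0 | 49.6 | 2.08 | 1,161 |

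Creatinine is in mg/dL. Under the printed form a man aged 60 stays above the upper limit of 75 until creatinine exceeds 2.46, and the lower limit of 20 could not exclude anyone in practice.

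**Step 3: the practical floor.** The minimum over ages 18 to 90, both sexes and both race terms at creatinine 15 is **40.2** (woman aged 90). Relaxing the assumptions gives 37.9 (woman aged 90, creatinine 20) or 37.5 (woman aged 100, creatinine 15). At creatinine 5 and age 90 the values are 50.6 (woman) and 52.4 (man). None of these approaches 20, and Stages 4 and 5 in SAP section 4.6 would be empty.

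**Step 4: the decline rules.** Creatinine rise needed above κ:

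- 15% fall: (1/0.85)^(1/0.209) = 2.18-fold
- 30% fall: (1/0.70)^(1/0.209) = 5.51-fold

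A doubling of creatinine, which SAP Appendix C flags as a laboratory change of interest, gives a fall of 1 - 2^-0.209 = 13.5%. That is below the protocol's own 15% trigger.

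**Step 5: size of the distortion, by assumption.** The documents give no other exponent. Their constants can be solved for the exponent that puts eGFR at 20 for an assumed creatinine of 2.5 to 4 mg/dL at ages 40 to 80; it runs from about -0.8 to -1.6. For an exponent -b, a 30% fall needs a (1/0.70)^(1/b)-fold rise, which the printed form reports as a fall of 1 - 0.70^(0.209/b).

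| Assumed exponent | Rise for a 30% fall | Fall shown by the printed form |
|---|---|---|
| -0.8 | 1.56-fold | 8.9% |
| -1.0 | 1.43-fold | 7.2% |
| -1.3 | 1.32-fold | 5.6% |
| -1.6 | 1.25-fold | 4.6% |

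**Step 6: alternative reading of the protocol text.** Taken literally as a subtraction, the protocol line makes eGFR rise with creatinine (about 157 at 1 mg/dL and 470 at 3 mg/dL, man aged 60). That reading does not rescue the formula.

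**The case against.** The best counter-argument is that this is a transcription error with no effect on the data. Eligibility is defined by the named CKD-EPI equation, not by the printed line. The protocol cites the publication and calls the equation validated, and the calculation belongs to the central laboratory. The SAP describes no derivation of eGFR from creatinine by the study programmers. The CKD stage table shows that the authors expected values below 30. A formula this unsuited to the population would probably have been noticed had it been run.

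Much of this stands. A misprint is a plausible explanation, and nothing in the documents shows that wrong values were produced. The primary UACR analysis does not use eGFR as endpoint or covariate. The floor of about 40 is practical rather than mathematical, and in the protocol the status of 0.209 as an exponent is inferred from a flattened superscript. The trial has also been terminated, so correcting the protocol changes no further conduct.

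The error in the specification remains. The SAP presents the printed line as the equation the laboratory applies, with the superscript intact, and the same digits in two documents make an extraction fault unlikely. Anyone checking eGFR against the SAP would code the wrong function, and no laboratory specification or check in either document settles what was run.

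**Conclusion.** The concern holds. The exponent as printed is incompatible with the 20 to 75 enrolment range and with the SAP's own CKD staging. The 558-fold, 2.18-fold and 5.51-fold figures follow from the printed exponent alone. The floor of 40.2 depends on the assumed creatinine ceiling of 15 mg/dL and age limit of 90, and the distortion in step 5 depends on the assumed alternative exponents.

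The effect on trial data is unknown: none if the laboratory ran the published equation, and material for every use of eGFR if it ran the printed one. SAP section 4.14 reports that "the total number of randomised participants is 613 with 340 participants completing treatment", so past eligibility and decline decisions cannot be changed. The final eGFR analysis and the deviation list still can. This should be fixed before the final analysis.

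**What to change.** 1. Replace the exponent in SAP section 3.2.1.2 and Protocol section 8.1.2.1 with the coefficient in the CKD-EPI publication that the protocol cites.
2. Obtain written confirmation from the central laboratory of the equation it coded, with its output for test creatinine values such as 1, 2 and 4 mg/dL in both sexes at a stated age.
3. If the printed form was used anywhere, recompute eGFR from stored creatinine before the final analysis. Then repeat the check of important protocol deviation 1 against the screening eGFR criterion.
4. If it was not used, correct the text only.

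The cost is one coefficient in each document and one laboratory confirmation, with no new samples. Re-issuing the protocol carries its usual administrative burden; since no conduct depends on it now, the SAP correction is the one that matters for the analysis. Recomputation arises only under item 3.
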